2. TYPE OF PLANNED ANALYSIS

2.1. Final Analysis

Final Analysis includes the time period from the first date of OL TDF dose through and including the date of last OL TDF dose plus 30 days. As a result of early study termination (FPFV July 2015 to LPLV April 2018) only two patients completed 96 weeks of observation on TDF treatment for HBV, the primary study objective to characterize the safety profile (renal and bone adverse outcomes) of subjects will be summarized based on available TDF exposure time. The assessment of efficacy and tolerability of TDF will be described. As most of the enrolled subjects were unable to complete the target observation period of 96 weeks, the final analysis will be unable to provide meaningful evidence to suggest whether enhanced or standard of care renal and bone monitoring frequencies between Group 1 and Group 2 offer early detection and mitigation of renal or bone adverse events. Instead, the data will be described by monitoring group and pooled together where possible.

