7.5.7. Management of ALT Flares

Flares on treatment: Spontaneous exacerbations in CHB are relatively common and are characterised by transient increases in serum ALT. After initiating antiviral therapy, serum ALT may increase in some patients. In patients with compensated liver disease, these increases in serum ALT are generally not accompanied by an increase in serum bilirubin concentrations or hepatic decompensation. Patients with cirrhosis may be at a higher risk for hepatic decompensation following hepatitis exacerbation, and therefore should be monitored closely during therapy.

Flares after treatment discontinuation: Acute exacerbation of hepatitis has also been reported in patients who have discontinued HBV therapy. Post-treatment exacerbations are usually associated with rising HBV DNA, and the majority appears to be self-limited. However, severe exacerbations, including fatalities, have been reported. Hepatic function should be monitored at repeated intervals with both clinical and laboratory follow-up for at least 6 months after

discontinuation of HBV therapy. If appropriate, resumption of HBV therapy may be warranted. In patients with advanced liver disease or cirrhosis, treatment discontinuation is not recommended since post-treatment exacerbation of hepatitis may lead to hepatic decompensation. Patients should be placed on commercially available HBV therapy following study drug discontinuation. Liver flares are especially serious, and sometimes fatal in patients with decompensated liver disease.

On-Treatment ALT Flare and Post-Treatment Exacerbation of Hepatitis are defined as:

- Serum ALT $> 2 \times$ baseline and $> 10 \times$ ULN, with or without associated symptoms OR
- Confirmed ALT elevation (defined as 1-grade shift or $2 \times$ previous value) associated with confirmed changes outside of the normal range in other laboratory parameters suggestive of worsening hepatic function (total bilirubin ≥ 2 mg/dL above baseline, abnormal PT ≥ 2 seconds or INR ≥ 0.5 over baseline, abnormal serum albumin ≥ 1 g/dL below baseline or elevated serum lactate levels (if available), defined as $2 \times$ ULN per the Adult AIDS Clinical Trials Group (AACTG) guidelines).

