
Study Duration
	
Subjects will be treated with TDF for 96 weeks. The duration for a given subject is at least 96 weeks plus 30 days to observe safety outcomes.
 
Subjects who permanently discontinue TDF will be asked to return for an end-of-treatment visit within 72 hours of the last dose of TDF. Subjects who permanently discontinue TDF will be followed for 24 weeks off treatment or up to initiation of active treatment, whichever occurs first.

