7.2. Laboratory Evaluations

Selected laboratory data (using conventional units) will be summarized by the observed data and change over time. Missing laboratory results for safety summaries will not be imputed. In all cases for laboratory evaluations, no inferential statistics will be computed.

Glomerular filtration rate (estimated creatinine clearance) will be calculated via statistical programming at each visit

(a) using Schwartz formula for subjects ages 12–18 years (ie, 12 to < 19) as follows:

$$\text{Schwartz formula (mL/min/1.73 m}^2\text{)} = k \times L/\text{Scr}$$

k is a proportionality constant,

k=0.55 for adolescent females 12-18 years old; and

k=0.70 for adolescent males 12-18 years old

L is height in centimeters (cm); and

Scr is serum creatinine (mg/dL)

(b) using Cockcroft-Gault equation for age ≥ 12 years as follows:

$$\frac{(140 - \text{age in years}) (\text{body weight [kg]})}{(72) (\text{serum creatinine [mg/dl]})}$$

[Note: multiply estimated rate by 0.85 for women; use actual body weight]

Creatinine clearance (CLcr) summaries will be provided by Schwartz and Cockcroft-Gault separately.

Summaries and data listings will use the Safety Analysis Set. For subjects who discontinue prior to the final week for the given analysis, all on-treatment laboratory data collected on or before the date of last dose + 7 days will be included in tabular summaries. Laboratory data prior to the first dose date of TDF will be included in data listings.

Summaries of laboratory data will be provided for the safety analysis set. No inferential statistics will be generated.

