7.2.2.1. Treatment-Emergent Laboratory Abnormalities

Treatment-emergent laboratory abnormalities are defined as values that increase at least one toxicity grade from baseline at any time post-baseline up to and including the date of last dose of TDF plus 30 days. If the relevant baseline laboratory data are missing, then any abnormality of at least Grade 1 will be considered treatment emergent.

Treatment-emergent laboratory abnormalities and Grade 3 or 4 treatment-emergent laboratory abnormalities by monitoring group and overall will be summarized based on the date of the abnormality. Abnormalities that occur prior to the first dose date of TDF or during follow-up will be included only in data listings.

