19.3.2	Treatment-Emergent Adverse Events Related to TDF	Grade 3 or 4 Bone or Renal Adverse Events	SAS
19.4	Treatment-Emergent Adverse Events	Leading to Permanent TDF Discontinuation	SAS
19.5	Treatment-Emergent Adverse Events	Leading to Change in Dose or Temporary Interruption of TDF	SAS
19.6	Treatment-Emergent Renal Adverse Events – Clinical Management and Outcomes Summary		SAS
19.7	Treatment-Emergent Bone-related Adverse Events – Clinical Management and Outcomes Summary		SAS
19.8	Treatment-Emergent Bone-related Adverse Events – Oral supplement use summary		SAS
19.9	Treatment-Emergent Serious Adverse Events		SAS
19.10	Treatment-Emergent Serious Adverse Events Related to TDF		SAS
20	Treatment-Emergent Adverse Events Occurring with >= 5% Incidence in Any Monitoring Group		SAS

Table Number	Title	Title	Analysis Set
21.1	Calcium (mg/dL) and Change from Baseline		SAS
21.2	Phosphorus (mg/dL) and Change from Baseline		SAS
21.3.1	Creatinine (mg/dL) and Change from Baseline		SAS
21.3.2	Creatinine Clearance (mL/min/1.73m ²) and Change from Baseline	Based on Schwartz	SAS
21.3.3	Creatinine Clearance (mL/min) and Change from Baseline	Based on Cockcroft-Gault	SAS
22.1	N-telopeptides (nmol BCE/L) and Change from Baseline		SAS
22.2	C-telopeptides (ng/mL) and Change from Baseline		SAS
22.3	Serum Osteocalcin (ng/mL) and Change from Baseline		SAS
22.4	Bone-Specific Alkaline Phosphatase (µg/L) and Change from Baseline		SAS
22.5	Serum PTH (pg/mL) and Change from Baseline		SAS
22.6	Vitamin D Level (25-hydroxy) (ng/mL) and Change from Baseline		SAS
23.1	Treatment-Emergent	Laboratory Abnormalities by Grade	SAS
23.2	Treatment-Emergent	Laboratory Abnormalities	SAS
23.3	Treatment-Emergent	Grade 3 or Grade 4 Laboratory Abnormalities	SAS
23.4	Treatment-Emergent	Marked Laboratory Abnormalities	SAS
24	Hepatic and Renal Related Abnormalities	Treatment-Emergent	SAS
25	On-Treatment ALT Flare and post treatment Exacerbation of Hepatitis		SAS
26.1	Cumulative Incidence of At Least a 4% Decrease from Baseline in Spine Bone Mineral Density (g/cm ²) by Week		SAS
26.2	Percent Change from Baseline in Spine Bone Mineral Density (g/cm ²) by Week	Categorical Summaries	SAS
26.3	Z-Scores for Spine Bone Mineral Density (g/cm ²) and Change from Baseline by Week	Categorical Summaries	SAS

Table Number	Title	Title	Analysis Set
27.1	Cumulative Incidence of At Least a 4% Decrease from Baseline in Whole Body Bone Mineral Density (g/cm ²) by Week		SAS

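### The SAP plans to report post-treatment hepatitis exacerbation, but its general data cut-offs keep most of the 24-week off-treatment follow-up out of the tables

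*SAP*

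**What the plan says.** **The outcome is planned.** SAP 7.2.2.3 defines the incidence of ALT flare and of post-treatment exacerbation, with one set of laboratory criteria for both and no time window. SAP Appendix 3 assigns it Table 25, "On-Treatment ALT Flare and post treatment Exacerbation of Hepatitis", on the Safety Analysis Set.

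**The follow-up is long.** SAP 1.2 states: "Subjects who permanently discontinue TDF will be followed for 24 weeks off treatment or up to initiation of active treatment, whichever occurs first". Protocol 7.5.7 says of the time after stopping HBV therapy: "Hepatic function should be monitored at repeated intervals with both clinical and laboratory follow-up for at least 6 months". It adds that severe and fatal exacerbations have been reported.

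**The data rules are short.**
- SAP 2.1 runs the Final Analysis from first dose "through and including the date of last OL TDF dose plus 30 days".
- SAP 7.2, for subjects who stop before the final week: "all on-treatment laboratory data collected on or before the date of last dose + 7 days will be included in tabular summaries".
- SAP 7.2.2.1 counts a laboratory abnormality as treatment-emergent if it arises "at any time post-baseline up to and including the date of last dose of TDF plus 30 days". Of abnormalities before first dose it says that these "or during follow-up will be included only in data listings".
- SAP Table 3-1 defines a Follow-up Week 24 window from last dose + 155 to last dose + 182 days. Nothing in Appendix 3 is assigned to it.

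**The protocol gives three rules.** Section 8.2.1.1 puts treatment-free follow-up data in the safety summaries, 8.2.1.2 uses treatment plus 30 days, and 8.6 puts treatment-free follow-up in listings. SAP 7.8 reports no alteration to the protocol's safety analysis, but does not say which of the three it follows.

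**The concern.** A post-treatment event can occur only after the last dose, yet the general rules close the tables 7 or 30 days after it. SAP 7.2.2.3 mentions an off-treatment value only as confirmation of a result first seen on treatment. It has no rule that admits a flare arising wholly off treatment. A programmer who applies the general rules would leave a flare at week 8 off treatment out of Table 25.

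Other tables do not fill the gap. Under protocol 7.3, non-serious adverse events are collected only if they are bone or renal, so a non-serious flare need not be recorded as an adverse event. A serious flare after day 30 is outside the treatment-emergent definition in SAP 7.1.5.1, and so outside Tables 19.9 and 19.10. Table 25 is the only planned summary for these events.

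At stake is a low or zero percentage that reads as a finding about stopping TDF when it partly reflects a data cut or absent measurements. Early stopping is the usual case here: of 30 enrolled subjects, two completed 96 weeks.

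**Working it through.** The plan states no figure of its own for this point, so there is none to reproduce. The check is day arithmetic and a comparison of rules.

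**Inputs**
- Off-treatment follow-up: up to 24 weeks (SAP 1.2) = 24 × 7 = 168 days.
- Cut-offs: last dose + 30 days (SAP 2.1 and 7.2.2.1) and last dose + 7 days (SAP 7.2).
- Follow-up Week 24 window: days 155 to 182 after last dose (SAP Table 3-1).
- Enrolled 30 (SAP 1.4); completed 96 weeks, 2 (SAP 2.1).

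**Share of a full follow-up left out of tables** = (168 − cut-off) / 168
- 30-day rule: 138/168 = 82.1% left out (19.7 weeks); 30/168 = 17.9% kept.
- 7-day rule: 161/168 = 95.8% left out (23.0 weeks); 7/168 = 4.2% kept.

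**Position of the follow-up window.** It opens 155 − 30 = 125 days after the 30-day cut-off and 155 − 7 = 148 days after the 7-day cut-off. No value in it can enter a table under either rule.

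**Denominator.** SAP 7.2.2.3 gives two for the same summaries: subjects with non-missing post-baseline values in the study period, and the whole Safety Analysis Set. Appendix 3 puts Table 25 on the Safety Analysis Set, so a subject with no ALT after last dose counts as event-free.

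**Subjects who could contribute.** 30 − 2 = 28 did not complete 96 weeks. This is an upper bound on the early stoppers with untreated follow-up, not a count of them.

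**Illustration only.** The documents give no distribution of time to flare. Assume exponential onset with median m days, so F(t) = 1 − exp(−t × ln 2 / m). The share of flares within 168 days that falls inside a cut-off c is F(c)/F(168):

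| Assumed median onset | Inside 30 days | Inside 7 days |
|---|---|---|
| 4 weeks | 53.2% | 16.2% |
| 8 weeks | 35.4% | 9.5% |
| 12 weeks | 29.2% | 7.5% |

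Over this range, and with full follow-up, the 30-day rule would miss about 47% to 71% of flares and the 7-day rule about 84% to 93%.

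**The case against.** The best counter-argument is that the specific outcome overrides the general rules. Table 25 has post-treatment events in its title, Table 3-1 supplies a follow-up window, SAP 7.2 speaks of on-treatment data, and SAP 7.2.2.1 governs graded treatment-emergent abnormalities rather than flares. The sponsor may well have meant Table 25 to use follow-up data. But the SAP does not say so, SAP 2.1 bounds the whole Final Analysis without exempting any table, and the window is attached to no output. The possible intent is a reason to write the exemption down.

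Other objections stand and limit the point.
- A reader might infer that all data after day 30 are discarded. They are not. Follow-up laboratory abnormalities and adverse events that are not treatment-emergent go to listings, and serious events of any organ class are reported, with listings of serious events and deaths (15.2 and 15.5). An ALT above 10 × ULN is Grade 4 and could appear in Listing 17.2.1.
- A reader might infer that all 28 early stoppers are the population at risk. The documents do not support this. Off-treatment follow-up ends when active treatment starts, and protocol 7.5.7 expects patients to go on to commercial HBV therapy. Many may have had little or no untreated time.
- Both procedure tables show only an adverse event check in the 30-day follow-up column and no liver chemistry after Week 96. That column may apply to completers and the 24 weeks to permanent discontinuers, so the two need not contradict each other, but the text does not say. Off-treatment ALT may be sparse.
- Flare is not a named objective or endpoint, and the final analysis is descriptive in 30 subjects. This lowers the consequence but does not make a misleading percentage acceptable.

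**Conclusion.** The point holds as a conflict between a planned output and the rules for its data. Followed as written, the SAP leaves most of a full off-treatment follow-up out of the only table meant to summarise post-treatment exacerbation: 82% under the 30-day rule and 96% under the 7-day rule. Together with the Safety Analysis Set denominator, this means the tabulated incidence can be too low.

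It is tempting to say that the incidence is biased to near zero. The documents do not support that. The percentages assume a subject observed for all 168 days, the number of such subjects is not given, the onset shares above rest on an assumed distribution, and the amount of off-treatment ALT is unknown. The direction of the error is clear if untabulated flares occurred; its size is not. The correction should be made before Table 25 is produced. It does not touch the bone or renal analyses.

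**What to change.** In SAP 7.2.2.3:
1. Exempt the post-treatment part of Table 25 from the + 7-day and + 30-day cut-offs.
2. Count events from the day after last dose to the end of off-treatment follow-up: 24 weeks, with the Table 3-1 window as the closing visit, or the start of other HBV therapy if earlier. Use every ALT in that span, because Table 3-1 has no follow-up window before day 155.
3. Use as denominator the subjects with at least one off-treatment ALT while not on other HBV therapy. Show that number and the off-treatment weeks observed, by monitoring group and overall.
4. Report on-treatment flares in a separate row.

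Reconcile SAP 2.1, 7.2 and 7.2.2.1 with this rule; the two denominators in 7.2.2.3; protocol 8.2.1.1, 8.2.1.2 and 8.6 on where follow-up data are reported; and the 30-day follow-up column in both procedure tables with the 24-week text.

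Cost: SAP wording and one revised table. If little off-treatment ALT was collected, the table will show that, and a zero will not be read as a zero rate. Appendix 3 names no full listing of off-treatment ALT, so the programmers should first confirm what the database holds.

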3. GENERAL CONSIDERATIONS FOR DATA ANALYSES

3.1. Analysis Sets

Analysis sets define which subjects are included in an analysis. Per International Conference on Harmonisation (ICH) E9, the intention-to-treat principle implies that the primary analysis should include all randomized subjects. It is recognized, however, that the ideal of complete follow-up of all randomized subjects is difficult to achieve. Therefore, the term “full analysis set (FAS)” will be used to identify the analysis set that is considered as close as possible to the intention-to-treat ideal of all randomized subjects.

The assignment of subjects to analysis sets will be done before the study blind is broken for analysis. A summary of the number and percentage of subjects in each analysis set will be provided by monitoring group and in total.

3.1.1. Randomized

The Randomized analysis set (RAS) includes subjects who were randomized into the study.

3.1.2. Full Analysis Set

The Full Analysis Set (FAS) includes subjects who were randomized into the study and received at least one dose of TDF.

3.1.3. Safety Analysis Set

The Safety Analysis Set includes subjects who were randomized into the study and received at least one dose of TDF. For this study there is no functional difference between FAS and the Safety Analysis Set.

3.1.4. Pharmacokinetics

Not applicable

3.2. Subject Groups

Subjects will be grouped for analyses according to randomized treatment for efficacy analysis using FAS. Subjects will be grouped according to actual treatment received for safety analysis using safety analysis set.

Unless otherwise specified, safety data will be summarized in tables by monitoring group as follows:

Group 1 – enhanced monitoring group, TDF

Group 2 – standard of care monitoring group, TDF

Pooled - All TDF

3.3. Strata and Covariates

Randomization was not stratified by age or region

3.4. Examination of Subject Subsets

Subgroup analyses were to be performed for the following secondary efficacy endpoints:

- Proportion with HBV DNA < 400 copies/mL (<69 IU/mL)
- Proportion with HBsAg loss

Subgroup analyses were to be performed for the following secondary safety endpoints:

- Subjects receiving dietary supplementation (e.g., Vitamin D, calcium, or phosphate)

3.5. Multiple Comparisons

No interim analysis of efficacy data will be performed prior to the Week 96 end of treatment analysis. Therefore no adjustment to the alpha level is required for this study.

3.6. Missing Data and Outliers

Missing Data

Missing data can have an impact upon the interpretation of the study data. In general, values for missing data will not be imputed. Sensitivity analyses will be performed if warranted.

A missing data point for a given study visit may be due to any of the following reasons:

- A visit occurred in the window but data were not collected or were unusable
- A visit did not occur in the window
- A subject permanently discontinued from the study before reaching the window.

Outliers

No special handling of outliers will be employed.

3.7. Data Handling Conventions and Transformations

HBV DNA levels will be measured using the Roche COBAS Taqman 48 assay, and values below the lower limit of quantitation (LLQ) for the assay will be set to the lower limit minus 1 (168 copies/mL [28 IU/mL]) for calculation of summary statistics for the actual HBV DNA values, change from study BL values by study visit. The original values will be provided in the HBV DNA listing.

For selected analyses, HBV DNA data (in copies/mL) will be transformed to the logarithmic (base 10) scale (\log_{10} copies/mL).

Both baseline and postbaseline borderline serology results will be imputed using the following rules:

- HBsAg and HBeAg borderline will be considered as HBsAg positive and HBeAg positive.
- HBsAb and HBeAb borderline will be considered as HBsAb negative and HBeAb negative.

For the determination of summary and order statistics, safety laboratory data that are continuous in nature but below the lower limit of quantitation or above the upper limit of quantitation will be imputed to the value of the lower or upper limit minus or plus 1 significant digit, respectively (eg, if the result of a continuous laboratory test is < 20 , a value of 19 will be assigned). Individual values that include symbols “ $<$ ” or “ $>$ ” will be presented as “ $<$ ” or “ $>$ ” in the data listings.

3.8. Visit Windows

3.8.1. Definition of Study Day 1

Study Day 1 is defined as the date of study baseline (BL). Study BL is defined as the first dose date of TDF. If the first dose of TDF date is missing, then it will be estimated by using the baseline visit date. In the event that data are missing for an endpoint at study BL, the last non-missing data collected prior to this study BL date will be used as study BL measurement. For subjects who have more than one value on the same study BL visit date, the mean (arithmetic or geometric, as appropriate) value will be used as the study BL value for continuous data, while the latest pre-dose value will be used as the study BL value for categorical data. For subjects who have more than one study BL value with different visit dates, the last value on or prior to the first dose date of TDF will be used as study BL.

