6.2. Pre-treatment Assessments

6.2.1. Screening Visit

Subjects will be screened within 30 days before assignment to determine eligibility for participation in the study. The following will be performed and documented at screening:

- 1) Obtain written informed consent
- 2) Obtain medical history
- 3) Complete physical examination including, vital signs, body weight, and height

- 4) Screen for pregnancy (serum screen) and contraceptive use
- 5) Conduct preliminary liver chemistry tests (ALT, ALP, AST, total and direct bilirubin, total protein, albumin, GGT, LDH, CK), serum renal chemistry (glucose, creatinine, creatinine clearance (calculated), magnesium, bicarbonate, chloride, potassium, sodium) and urinalysis (glucose, protein, creatinine, phosphate, bicarbonate, blood, calcium) (to be averaged with Baseline renal chemistry values), fasting required
- 6) HBV serology (HBeAg and HBsAg; anti-HBe and anti-HBs (if Ag negative))

Subjects meeting all of the inclusion criteria and none of the exclusion criteria will return to the clinic within 30 days after screening for commencement into the study.

From the time of obtaining informed consent through the first administration of Tenofovir DF, record all renal and bone AEs and any SAEs (not limited to bone or renal) on the adverse events case report form (CRF/eCRF). All other untoward medical occurrences observed during the screening period, including exacerbation or changes in medical history are to be captured on the medical history CRF/eCRF. See Section 7 Adverse Events and Toxicity Management for additional details.

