6.3. Baseline Visit

The Baseline Visit should occur within 30 (\pm 3) days of the initial Screening Visit. All baseline tests and procedures should be completed prior to the receipt of the first dose of Tenofovir DF. Subjects will be dispensed Tenofovir DF medication at their Baseline Visit. Tenofovir DF should be initiated within 24 hours of the Baseline Visit.

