7.2.2.3. Summaries of Laboratory Abnormalities

The following summaries (number and percentage of subjects) of laboratory abnormalities will be provided by monitoring group (subjects categorized according to most severe abnormality grade), where applicable:

- Treatment-emergent laboratory abnormalities
- Treatment-emergent marked laboratory abnormalities

For all summaries of laboratory abnormalities, the denominator is the number of subjects with non-missing post-baseline values in the given study period. A listing of treatment-emergent Grade 3 or Grade 4 laboratory abnormalities will be provided.

Incidence of ALT flare and post-treatment exacerbation of hepatitis is defined as follows:

- Serum ALT $> 2 \times$ study BL and $> 10 \times$ ULN, with or without associated symptoms

OR

- Confirmed ALT elevation (defined as 1-grade shift [ie, increase] or $2 \times$ previous value) with confirmed changes outside of the normal range in other laboratory parameters suggestive of worsening hepatic function (total bilirubin ≥ 2 mg/dL above study BL, abnormal prothrombin time ≥ 2 seconds over BL or international normalized ratio [INR] ≥ 0.5 over BL, abnormal serum albumin ≥ 1 g/dL below BL or elevated serum lactate levels [if available], defined as $2 \times$ ULN).

Summaries (number and percentage of subjects) of treatment-emergent, on-treatment laboratory abnormalities will be provided by monitoring group and overall, with the following modifications for the creatinine summaries:

Confirmed (defined as 2 consecutive visits) increase in serum creatinine of 0.3 mg/dL above BL

Confirmed (defined as 2 consecutive visits) increase in serum creatinine of 0.5 mg/dL above BL.

A confirmed laboratory results is defined as either being present at 2 consecutive visits or at the last visit. If the first of 2 consecutive results is on-treatment and the second is off-treatment, then the result is considered confirmed.

For all summaries of laboratory abnormalities, the denominator is the number of subjects in the Safety Analysis Set.

Hepatic flares will be summarized by monitoring group and overall.

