7.8. Changes From Protocol-Specified Safety Analyses

No alterations to the protocol-specified safety analysis have been made. The study has been canceled due to low enrolment and due to the approval of TAF for HBV in adolescents in November 2016 as a safer treatment option for patients. With two subjects completing 96 weeks of treatment the safety analysis will shift to focus on subjects' available treatment exposure to TDF.

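### The SAP's baseline rule drops the screening renal chemistry that the protocol says to average into baseline, and does not declare the departure

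*SAP*

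**What the plan says.** Protocol 6.2.1 lists serum renal chemistry among the screening tests and notes that the results are "to be averaged with Baseline renal chemistry values". Section 6.3 places the Baseline Visit within about 30 days of Screening, and Appendix 2 schedules serum renal chemistry at both visits for both monitoring groups.

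SAP 3.8.1 has three rules for baseline:
- Same date: continuous results are averaged.
- Different dates: "the last value on or prior to the first dose date of TDF will be used as study BL".
- Baseline value missing: "the last non-missing data collected prior to this study BL date will be used as study BL measurement".

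None of these makes an exception for renal chemistry. SAP 7.8 states: "No alterations to the protocol-specified safety analysis have been made".

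The baseline feeds the change-from-baseline summaries (SAP 7.2.1; Tables 21.3.1 to 21.3.3 for creatinine and clearance), the grade-shift definition of treatment-emergent abnormalities (7.2.2.1), and the creatinine counts in 7.2.2.3. The first of those counts is "Confirmed (defined as 2 consecutive visits) increase in serum creatinine of 0.3 mg/dL above BL"; the second uses 0.5 mg/dL. The same section also accepts a rise as confirmed if it is present at the last visit.

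**The concern.** Screening and Baseline normally fall on different dates, so the different-dates rule applies to almost every subject and the screening sample goes unused. Each renal change then carries the full error of one pre-dose sample.

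Confirmation does not remove that error. A chance-low baseline is shared by all later visits, so it raises the apparent change at two consecutive visits together. Through the last-visit route, one post-baseline value is enough.

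Documenting renal laboratory abnormalities is a secondary objective. With 15 subjects per group (SAP 1.4), one spurious case moves a group percentage by 1/15 = 6.7 points.

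**Working it through.** Neither document gives a figure for the precision of renal change, so there is no stated number to reproduce.

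**Inputs**
- Creatinine change in the earlier adolescent CHB trial, TDF arm, Week 72: mean 0.1, SD 0.10 (Protocol 1.2.3.1). The unit is taken as mg/dL. That trial's baseline rule is not given, so the SD is used for scale only and treated as the single-baseline SD.
- Actual enrolment: 30, 15 per group (SAP 1.4).
- Assumption: within-subject errors have equal variance s² and are independent unless stated otherwise.

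**Variance of a change**
- One baseline: s² + s² = 2s².
- Mean of two baselines: s² + s²/2 = 1.5s².
- Variance ratio 1.5/2 = 0.75; SD ratio √0.75 = 0.866, a 13.4% reduction.

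**When only part of the variance is error**

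Let f be the share of single-baseline change variance due to within-subject error. Then 2s² = f, averaging removes s²/2 = f/4, and the variance ratio is 1 − f/4. The last column is the normal-approximation 95% half-width for a group mean, 1.96 × SD/√15; with one baseline it is 0.051.

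| f | SD ratio | SD (from 0.10) | Half-width, n = 15 |
|---|---|---|---|
| 1.00 | 0.866 | 0.087 | 0.044 |
| 0.75 | 0.901 | 0.090 | 0.046 |
| 0.50 | 0.935 | 0.094 | 0.047 |
| 0.25 | 0.968 | 0.097 | 0.049 |

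The reductions for the last three rows are 9.9%, 6.5% and 3.2%. If instead the screening and baseline errors have correlation ρ, the variance ratio is (1 + (1 + ρ)/2)/2. Values of ρ of 0.25, 0.5 and 0.75 give the same three reductions, and ρ = 1 gives none.

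**Chance of crossing +0.3 mg/dL at one visit, mean rise 0.1**
- One baseline: P(Z > (0.3 − 0.1)/0.10) = P(Z > 2.00) = 2.3%.
- Mean of two, f = 1: P(Z > 0.2/0.0866) = P(Z > 2.31) = 1.0%.
- Mean of two, f = 0.75, 0.50, 0.25: 1.3%, 1.6%, 1.9%.

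**Chance of crossing +0.3 at a given pair of consecutive visits, f = 1**
- The two changes share the baseline error. Their correlation is s²/(2s²) = 0.5 with one baseline and (s²/2)/(1.5s²) = 1/3 with two.
- Bivariate normal: both above 2.00 at correlation 0.5 gives 0.41%; both above 2.31 at correlation 1/3 gives 0.07%.

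**Expected subjects among 30, f = 1**
- Per pair of visits: 30 × 0.41% = 0.12 against 30 × 0.07% = 0.02.
- Last-visit route: 30 × 2.3% = 0.7 against 30 × 1.0% = 0.3.

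**Chance of crossing +0.5 at one visit, f = 1**
- P(Z > 4.00) = 0.003% with one baseline and P(Z > 4.62) = 0.0002% with two. Both are negligible.

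**The case against.** The best case for leaving the SAP alone has five parts.

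1. **The averaging note is isolated.** It appears once, in a list of screening procedures. It is not repeated under Baseline Assessments, in the schedule or in Protocol Section 8, where the safety analysis uses change from baseline without defining a renal baseline. The statement in SAP 7.8 can therefore be read as literally true of Section 8. This softens the criticism of 7.8, but the note is a direct instruction on how renal values are combined and the SAP does not follow it.
2. **The large figures are upper bounds.** A 72-week change in adolescents probably contains real change; the placebo arm of the earlier trial also rose by 0.1 (SD 0.09). This stands, and is why the range matters more than the 13%.
3. **No inference depends on it.** The study stopped early, two subjects completed 96 weeks, and SAP 7.2 computes no inferential statistics for laboratory data. This stands.
4. **Averaging has its own drawback.** Renal chemistry at screening also serves the creatinine clearance criterion for entry, so chance-high screening creatinines are preferentially excluded and an averaged baseline may be slightly low. The documents do not allow the size to be estimated. A summary on the last pre-dose value would show whether it matters.
5. **An averaged value has no laboratory-assigned grade,** and averaged clearance need not equal clearance from averaged creatinine. Both are settled by stating a rule.

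A reader might go further and infer that every renal change is affected. The documents do not support that. The protocol note names renal chemistry values, phosphorus belongs to the bone panel, which the protocol does not schedule at screening, and dipstick urinalysis is categorical. A reader might also take the fall from 2.3% to 1.0% as the effect on the SAP's confirmed count. It is a single-visit, all-error figure and applies only to the last-visit route.

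**Conclusion.** The mismatch is real, undeclared and worth correcting; its numerical effect is modest. It adds noise to changes in serum renal chemistry and calculated creatinine clearance, and to the 0.3 mg/dL count. The 0.5 mg/dL count is practically unaffected. Averaging would reduce the SD of change by at most 13.4%, and by 3.2% to 9.9% over the range of error shares examined. These figures assume equal error variances. The maximum also needs independent errors and no true variation in change, and the threshold probabilities further assume normality and the scale borrowed from the earlier trial.

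A reader might infer that the rule biases the comparison of monitoring groups. It does not by itself do so, because the same rule applies to both groups and both have the two pre-dose samples scheduled. It is also too strong to say that the SAP never averages pre-dose values: it does so for the same date, although that does not bring in the screening sample. What is at stake is precision in a descriptive analysis of 30 subjects, and agreement between the two documents.

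**What to change.** In SAP 3.8.1 add an exception for continuous serum renal chemistry:
- Study baseline is the mean of the Screening and Baseline Visit values, or the available one if the other is missing.
- Baseline creatinine clearance is computed from the mean creatinine.
- Baseline toxicity grade is derived from the averaged value.

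Add a listing or sensitivity summary using the last pre-dose value, to cover the eligibility effect. If the sponsor keeps the single-value rule for any parameter, 7.8 should say so and give the reason.

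Protocol 7.5.4 refers to creatinine above baseline without saying how that baseline is formed. That wording must be reconciled with the definition used.

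The cost is a few sentences and a small amount of programming. No new data are needed.
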